COVER PAGE FOR PROTOCOL AND STATISTICAL ANALYSIS PLAN

Official Study Title: SGLT2 Inhibition and Stimulation of Endogenous Glucose Production:
Protocol 2

NCT number: NCT02592421

IRB Approval Date: 09/06/2017

Protocol Template Form

Item 1 UTHSCSA Tracking Number	HSC20150668H
-----------------------------------	--------------

Item 2 Abstract / Project Summary	
Provide a succinct and accurate description of the proposed research. State the purpose/aims. Describe concisely the research design and methods for achieving the stated goals. This section should be understandable to all members of the IRB, scientific and non-scientific.
 
DO NOT EXCEED THE SPACE PROVIDED.

------------------------------------------	---------------------------------------------------------------------------------------------------------------------------------------------------------------------------------------------------------------------------------------------------------------------------------------------------------------------------------------------------------------------

Purpose/Objectives: We will determine the role of pancreatic hormones (increase in plasma glucagon and decrease in plasma insulin concentration) in the stimulation of EGP following SGLT2 inhibition.

Research Design/Plan: After screening, eligible subjects will receive three 5-hour measurements of EGP with administration of study drug after a 3-hour tracer equilibration period. HGP will be measured for 5 hours after drug administration to allow sufficient time for a significant increase in HGP above baseline after dapagliflozin administration (10). In study 1, HGP will be measured for 5 hours after dapagliflozin (10 mg) or placebo administration. Study 2 will be performed under glucose clamp conditions (i.e. maintaining the plasma glucose concentration stable at each subject's fasting level), and Study 3 will be performed under pancreatic clamp conditions (maintaining the plasma glucagon and insulin concentrations constant at the basal level). Subjects will be randomized in a 2:1 ratio; 20 subjects will receive dapagliflozin and 10 subjects will receive placebo. Each study will be performed on a separate day, after a 10-12 hour overnight fast within 1-2 week period.

Methods: Screening visit; Study 1 EGP, Study 2 EGP with Glucose Clamp, Study 3 EGP Pancreatic Clamp

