Type 2 Diabetic subjects	18-70 yrs old BMI = 25-45 kg/m ² HbA1C < 10% Other than diabetes, subjects must be in good general health as determined by physical exam, medical history, blood chemistries, CBC, TSH, T4, EKG and urinalysis Only subjects whose body weight has been stable (\pm 3 lbs) over the preceding three months and who do not participate in an excessively heavy exercise program will be included.	Subjects taking drug known to affect glucose metabolism (other than metformin and sulfonylurea) Individuals with evidence of proliferative diabetic retinopathy, plasma creatinine >1.4 females or >1.5 males, or 24-hour urine albumin excretion > 300 mg will be excluded.

Item 6

Research Plan / Description of the Research Methods a. *Provide a comprehensive narrative describing the research methods. Provide the plan for data analysis (include as applicable the sample size calculation).*

Step-by-Step Methods: Screening Visit. Medical history is obtained and physical exam performed. Blood is drawn for FPG, blood chemistries, lipid profile, HbA1c, and thyroid function. Urine analysis, EKG and pregnancy test are performed.

Study 1: Effect of Dapagliflozin on EGP: EGP will be measured with 3-³H-glucose infusion. The 3-³H-glucose infusion will be started at 6 AM and arterialized blood samples will be drawn from a catheter placed retrogradely in a vein on the dorsum of the hand to measure the basal rate of EGP. The hand will be placed in a box heated to 70°C to ensure arterialization of the venous blood. After a 3 hour tracer equilibration period (at 9 AM) subjects will receive dapagliflozin (10 mg) or placebo, and blood samples will be drawn every 10-20 minutes for 5 hours (until 2 PM) for the measurement of plasma glucose, insulin, C-peptide, glucagon, cortisol, catecholamine concentrations and [3-³H]-glucose specific activity. Urine will be collected from 6 to 9 AM and from 9 AM to 2 PM. Urinary volume and glucose conc will be measured and the rate of urinary glucose excretion quantitated. The study will end at 2 PM and subjects will be allowed to return home. Basic metabolic panel will be performed during the study to monitor renal function.

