Data Analysis Plan: Data Analysis and Statistical Methods: Under steady-state postabsorptive conditions, the basal rate of endogenous glucose appearance ($R_a = bEGP$) equals the 3-³H-glucose infusion rate divided by steady state plasma tritiated glucose specific activity. After drug administration, non-steady conditions for 3-³H-glucose specific activity prevail and the rate of whole body glucose appearance (R_a) is calculated from Steele's equation. During the glucose clamp study, the rate of EGP after drug administration equals R_a minus glucose infusion rate, while, during the pancreatic clamp, $R_a = EGP$ since no cold glucose is infused. The difference in EGP during the last hour of the study (240-300 minute) between subjects receiving dapagliflozin and subjects receiving placebo represents the increase in EGP caused by dapagliflozin (glucosuria-stimulated increase in EGP). The glucosuria-stimulated increase in EGP will be compared among the three studies with ANOVA. Post hoc testing will be performed with a Bonferroni correction for multiple comparisons. The difference in glucosuria-stimulated increase in EGP between study 2 and study 1 represents the contribution

of the decrease in plasma glucose conc to the increase in EGP, while the difference between study 3 and study 1 represents the contribution of change in islet hormones (insulin/glucagon) to the increase in EGP.

Item 7 Risks Section:

Complete the following table to describe the risks of all **research procedures** listed in Step 2, Institutional Form (items 28-34). *Do not list risks of Routine care procedures here.*

N/A, Risks are described in the informed consent document – do not complete this table.

Research procedures	Risks
example: 
• History and physical• Questionnaire• Laboratory tests	List the reasonably expected risks under the following categories as appropriate:
Add or delete rows as needed	

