EGP measurement with 3- ³ H-glucose	
 ○ Blood draws and cath placement: 
 ○ fainting, pain, bruising, swelling, bleeding, anemia or rarely infection where the needle is inserted. ○ In rare cases the area where the needle is inserted can also become infected or nerves may be damaged, inducing long-lasting abnormal sensations (paresthesia), impaired sensation of touch and persistent pain ○ Some people may experience mild pain from the catheter. On rare occasions, inflammation of the vein may occur or bruising or black and blueness may occur over the puncture site. Such complications occur in less than 1% of individuals and, if they occur, they usually go away on their own in 2-3 days and are helped by using hot packs. ○ Radiation exposure 
There is no known minimum level of radiation exposure that is recognized as being totally free of the risk of causing genetic defects (abnormal cells) or cancer. However, the probability of harm from such risk associated with the amount of radiation exposure received from this study is considered to be low when compared to other everyday risks each member of the general public receives per year, depending on the
 ○ Heated box: 
During visits 2, 3, and 4 , the hand is placed in a transparent plastic thermo regulated box heated to 70°C (158°F). Rarely, the hand may suffer a burn or blister. Please tell us if your hand is too hot or feels uncomfortable while in the heated box, in which case your hand will be removed from the box but the test will be continued.
 ○ Dapagliflozin: 
 ○ Likely and not serious: ○ These risks are expected to occur in more than 20 out of 100 subjects: Nausea ○ ○ Less likely and not serious: ○ These risks are expected to occur in 5-20 subjects or less out of 100 subjects: vomiting, diarrhea, constipation, GI upset, dizziness, fatigue, headache, runny nose, and in less than 4 out of 100 individuals low blood sugar (also called Hypoglycemia), urinary tract (about 1%) and genital infections (about 4%) ○ ○ Rare and serious: loss of consciousness (or syncopy), decrease in blood pressure (less than 1%), and bladder cancer (less than 0.2%). ○ ○ Safety considerations for dapagliflozin and other SGLT2 inhibitors: ○ Dapagliflozin – is a sodium-glucose cotransporter 2 (SGLT2) inhibitor indicated as an adjunct to diet and exercise to improve glycemic control in adults with type 2 diabetes mellitus and is a member of a class of antidiabetic medications that work by increasing the glucose excretion in the urine. Dapagliflozin (FARXIGA) has been approved by the U.S. FDA. Side effects reported with dapagliflozin will be summarized below based upon http://www1astrazeneca-us.com/pi/pi_faxiga.pdf ○ ○ Hypotension ○ Dapagliflozin may cause intravascular volume contraction. Symptomatic hypotension can occur after initiating dapagliflozin particularly in patients with impaired renal function (eGFR less than 60 ±5 mL/min/1.73 m²), elderly patients, or patients on loop diuretics. Subjects with eGFR less than 60 ±5 mL/min/1.73 m² will not be allowed in the study. Signs and symptoms of hypotension after initiating therapy will be monitored. If a participant experiences any of these, the dapagliflozin will be stopped and the participant will be discontinued from the study. ○ Renal Function ○ A small decrease in kidney function (eGFR) and increase in serum creatinine has been observed when dapagliflozin is initially started. The eGFR gradually returns toward normal while the drug is continued and returns to normal if drug is stopped. If the eGFR drops below 60 or if the serum creatinine rises by ≥3.0 mg/dl the dapagliflozin will be stopped and the participant will be discontinued from the study. Sudden kidney injury (acute kidney injury) has happened to people taking dapagliflozin. Talk to your doctor right away if you: 
 ○ reduce the amount of food or liquid you drink for example, if you are sick or cannot eat or ○ you start to lose liquids from your body for example, from vomiting, diarrhea or being in the sun too long. Seek medical attention immediately if you experience signs and symptoms while taking these medicines such as: 
 ○ Decreased urine ○ Swelling in your legs or feet ○ Hypoglycemia ○ Hypoglycemia (low blood sugar) – can occur with any antidiabetic medication. In studies of dapagliflozin, the frequency of hypoglycemia was less than 5% and similar to that in the placebo group. Subjects will be told to call the investigator if symptoms (sweating, rapid thumping heartbeat, mental confusion) of hypoglycemia occur and to drink a glass of orange juice with a packet of sugar. Any subjects with hypoglycemia will be evaluated for potential causes. If the hypoglycemia recurs, the subject will be discontinued from the study.

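### Neither the order nor the minimum spacing of the three dosed study days is stated; randomising the order within each arm is a cheap safeguard against carryover of active drug

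*Combined protocol and SAP*

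**What the plan says.** Item 2 (Research Design/Plan) describes one randomisation, of drug: "Subjects will be randomized in a 2:1 ratio; 20 subjects will receive dapagliflozin and 10 subjects will receive placebo". Each subject has three EGP measurements with study drug, and Item 6 gives dapagliflozin or placebo at 9 AM in each of Studies 1, 2 and 3. The only scheduling rule is "Each study will be performed on a separate day, after a 10-12 hour overnight fast within 1-2 week period".

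Two places hint at an order without setting one. The Methods line of Item 2 reads "Screening visit; Study 1 EGP, Study 2 EGP with Glucose Clamp, Study 3 EGP Pancreatic Clamp", and the heated-box entries in the Item 7 risk table say "During visits 2, 3, and 4" without tying a study to a visit. No washout or minimum interval is given.

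In the Data Analysis Plan of Item 6, the effect within a study is the dapagliflozin-placebo difference in EGP at 240-300 minutes. Then "The glucosuria-stimulated increase in EGP will be compared among the three studies with ANOVA", with Bonferroni-corrected post hoc tests. No visit, sequence or carryover term is named. Study 2 against Study 1 is read as the contribution "of the decrease in plasma glucose conc to the increase in EGP", and "the difference between study 3 and study 1 represents the contribution of change in islet hormones (insulin/glucagon) to the increase in EGP".

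A pre-dose sample exists on every study day: "Urine will be collected from 6 to 9 AM and from 9 AM to 2 PM". Basal EGP is also measured before each dose.

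**The concern.** Both contrasts that carry the mechanistic conclusion compare one study day with another. The placebo arm protects them against anything that changes from day to day in both arms alike. It does not protect them against something only the dapagliflozin arm can have: residual effect of active drug from a preceding study day.

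If the days run in the listed order, the number of preceding active doses rises in step with the study number. Carryover would then sit inside the Study 2 minus Study 1 and Study 3 minus Study 1 contrasts and be reported as a contribution of the glucose fall or of islet hormones. No later analysis of the same outcome could separate the two, whereas a randomised order set before the first subject could.

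**Working it through.** **Inputs.** From the document: 20 dapagliflozin and 10 placebo subjects (20:10 matches the stated 2:1), three dosed days each, and the two contrasts above, written 2-1 and 3-1. The document gives no order, gap, carryover size, SD or power, so there is no plan figure to reproduce. Everything numerical about carryover below is illustrative. Signs reverse if carryover is negative.

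**Preceding active doses, listed order.** Dapagliflozin arm 0, 1, 2 for Studies 1, 2, 3; placebo arm 0, 0, 0.

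**Can it be separated afterwards?** Subject (30), study (2) and drug-by-study (2) terms make 34 columns. Adding visit (2) and drug-by-visit (2) makes 38. In listed order visit and study are the same variable, so the rank stays at 34 of 38 and neither drug-by-study contrast is estimable. In a balanced order the rank is 38 of 38.

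**Shift under first-order carryover.** Let a fraction c of the preceding day's drug effect carry over. Set the Study 1 effect to 100, and let the Study 2 and 3 effects, e2 and e3, lie between 0 and 100.

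- Listed order: 2-1 shifts by 100c and 3-1 by c·e2. At c = 10% that is 10 and 0 to 10; at 30%, 30 and 0 to 30.
- Balanced order, example list: sequences 123, 132, 213, 231, 312, 321 used 4,3,3,3,3,4 times on dapagliflozin and 1,2,2,2,2,1 times on placebo. On dapagliflozin, Study 1 is preceded by Study 2 in 7 subjects and by Study 3 in 6. Study 2 is preceded by Study 1 in 7 and by Study 3 in 7. Study 3 is preceded by Study 1 in 6 and by Study 2 in 7.
  - 2-1: c(700 + e3 - 7·e2)/20, at most 40c, which is 4.0 at 10% and 12.0 at 30%.
  - 3-1: c(600 - 6·e3)/20, at most 30c, which is 3.0 at 10% and 9.0 at 30%.
- Exception: if e2 = 0, listed order leaves 3-1 unshifted (c·e2 = 0), while balancing can add up to 3.0 points at 10%.

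**Shift under a constant 10 points per preceding dose.** Listed order: 10 and 20. Example list: mean preceding doses are 1.0 in every study, so 0 and 0.

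**What extra model terms add (example list).**

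| Model | SE of 2-1, 3-1 (residual SD) | df |
|---|---|---|
| No visit terms | 0.548, 0.548 | 56 |
| Visit and drug-by-visit | 0.554, 0.548 | 52 |
| Plus preceding study, dapagliflozin arm only | 0.579, 0.566 | 50 |
| Plus preceding study, both arms | 0.613, 0.627 | 48 |

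The first row is sqrt(2 × (1/20 + 1/10)) = 0.548, with 90 - 34 = 56 df. Drug-by-visit terms lower the worst shift at 10% only from 4.0 and 3.0 to 3.6 and 3.0. Both preceding-study models bring the two carryover illustrations to 0. Under a 10-point after-effect of one study that is common to both arms, however, the dapagliflozin-only version is off by up to 3.3 and 4.0 points; the both-arms version stays at 0.

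**What balancing gives up.** In listed order, after-effects common to both arms cancel exactly. With the example list they do not quite cancel. For a 10-point after-effect of Study 3, 2-1 moves by 10 × (7 - 6)/20 = 0.5 on dapagliflozin and by 10 × (3 - 4)/10 = -1.0 on placebo, a net 1.5; for 3-1 the net is -3.0 - (-4.0) = 1.0. Doubling the placebo list for dapagliflozin (2,4,4,4,4,2 against 1,2,2,2,2,1) makes the proportions identical and restores exact cancellation. Its carryover shifts are c(600 - 6·e2 - 2·e3)/20 and c(800 - 8·e3)/20, so -1.0 to 3.0 and 0 to 4.0 at 10%. The constant-per-dose shift stays 0.

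**Spacing.** If the window covers all three days, they may be consecutive. The largest achievable minimum gap is 3 days in a 7-day window (days 1, 4, 7) and 6 days in a 14-day window (days 1, 7, 13). With an assumed half-life of effect h between 6 and 48 hours, the residual 2^(-gap/h) is 6% to 71% at 24 hours, 0.02% to 35% at 72 hours, and about 0% to 12.5% at 144 hours.

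**Pre-dose check.** Comparing arms on one study day, the 95% half-width is 2.048 × sqrt(1/20 + 1/10) = 0.79 SD, with 80% power only for a difference of 1.12 SD.

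**The case against.** The strongest reply is that the harm rests on two unknowns. The listed order is an assumption: the Methods line is a list of procedures, not a schedule. Carryover may be negligible, especially if the days are well apart. Both points stand. A reader might infer that the plan's mechanistic contrasts are confounded with order, or biased. The document does not support that, because it assigns no order and gives no carryover figure. If the order varied from subject to subject, the exact aliasing would disappear, although unplanned variation need not be balanced or alike in the two arms.

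The spacing phrase most naturally covers all three days, but it could mean the interval between days, in which case a minimum gap already exists. This stands too, and is why the first request is to clarify the sentence.

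Listed order also has a merit: after-effects common to both arms cancel. That is not trivial, since Study 3 runs somatostatin, insulin and glucagon from 5:45 AM to 2 PM in everyone. Closely matched sequence proportions answer most of this, and identical proportions answer all of it.

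Subtracting same-day basal EGP would remove carryover that is constant through the day, whatever the order. It would not repair a blunted response to the new dose, so it complements a balanced order without replacing it.

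Finally, the Study 3 text repeats the 2:1 ratio, from which a reader might infer a fresh randomisation each day. The 20 and 10 subject counts in Item 2 point to one allocation per subject.

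**Conclusion.** The point holds as a recommended safeguard. It is certain that the plan randomises drug only and states neither an order nor an unambiguous minimum gap, while reading differences between study days as mechanism. It is conditional that, in listed order, carryover of active drug would be inseparable from those differences. Whether carryover exists, its sign, and which contrast it would affect more cannot be determined from the document.

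Balancing the order is the main protection. It removes the shift under a constant per-dose effect and reduces it in most first-order cases, but not in all, as the zero-Study 2-effect case shows. Visit and drug-by-visit terms add little beyond it.

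**What to change.** 1. Clarify whether the 1-2 week period spans all three study days or separates them, and state a minimum interval chosen and justified by the sponsor.
2. Randomise the order of the three study days in balanced fashion within each arm, from one list of 30 arm-and-sequence slots, with sequence proportions as similar between arms as 20 and 10 allow. Either list in the working would serve; the doubled one matches the arms exactly. Record order and dates.
3. Treat visit and drug-by-visit terms as optional (example list: at most 1.2% in SE, 4 df). If a preceding-study sensitivity model is used, put its terms in both arms (example list: up to 14.5% in SE, 8 df), not in the dapagliflozin arm alone.
4. On each study day compare the arms on pre-dose urine glucose and basal EGP, with confidence intervals, as a low-power check whose null result does not exclude carryover. Compare within the same study day, because the Study 3 pre-dose period is already under somatostatin.
5. Report change from same-day basal EGP as a sensitivity analysis, stating that it does not correct a blunted response.

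The cost is an order list and harder booking of clamp days. With the near-uniform example list, exact cancellation of common after-effects is also lost (about 1 to 1.5 points per 10). No extra visits, subjects or samples are needed.

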- During clinical trials, the overall proportion of subjects with malignant or unspecified tumors was similar between those treated with dapagliflozin (1.47%) and placebo/comparator (1.35%), and there was no carcinogenicity or mutagenicity signal in animal data. When considering the cases of tumors occurring in the different organ systems, the relative risk associated with dapagliflozin was above 1 for some tumors (bladder, prostate, breast) and below 1 for others (e.g. blood and lymphatic, ovary, renal tract), not resulting in an overall increased tumor risk associated with dapagliflozin. The increased/decreased risk was not statistically significant in any of the organ systems. If you have a prior history of bladder, prostate, or breast cancer please tell us.
- Bladder Cancer
- Of 22 clinical studies, newly diagnosed cases of bladder cancer were reported in 0.17% of patients treated with dapagliflozin and 0.03% treated with placebo/comparator. After excluding patients in whom exposure to study drug was less than one year at the time of diagnosis of bladder cancer, there were 4 cases with dapagliflozin and no cases with placebo/comparator. Bladder cancer risk factors and hematuria (a potential indicator of pre-existing tumors) were balanced between treatment arms at baseline. There were too few cases to determine whether the emergence of these events is related to dapagliflozin. . Any subject with a prior history of bladder, prostate, or breast cancer will be excluded from the study. Any subject with hematuria will be excluded from the study. Hematuria will be examined yearly and worked up for etiology.
- Bone Health
- Bone mineral density measurements in patients with normal or mildly impaired renal function did not indicate bone loss over a treatment period of one year, and there was no increase in fracture risk in these individuals with normal or mildly impaired renal function. However, it cannot be excluded that with longer periods of treatment there will be a decrease in bone mineral density or increase in bone fracture risk.
- If you experience a bone fracture contact the study doctor.
- LDL Cholesterol
- A small increase in LDL cholesterol of about 4% has been observed in diabetic patients treated with dapagliflozin.
- Cardiovascular Events

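### The eGFR entry limit in Item 7 has no single value (60 ±5), one reading puts it below the exact stopping value of 60, and Item 5 does not list it

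*Combined protocol and SAP*

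**What the plan says.** Item 5 (study population) has two renal exclusions. One is on creatinine, "plasma creatinine >1.4 females or >1.5 males", with no unit. The other is on albuminuria: "24-hour urine albumin excretion > 300 mg will be excluded". The inclusion column adds that "subjects must be in good general health as determined by physical exam, medical history, blood chemistries" and further tests, without an eGFR figure.

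The Item 7 risk table has one row for each of the three EGP procedures, and the same dapagliflozin text appears in each. Under Hypotension it says that symptomatic hypotension can occur "particularly in patients with impaired renal function (eGFR less than 60 ±5 mL/min/1.73 m²"), and then sets the entry rule: "Subjects with eGFR less than 60 ±5 mL/min/1.73 m² will not be allowed in the study". Under Renal Function, the next paragraph, it says that a small fall in eGFR is seen when dapagliflozin is started, and gives the stopping rule: "If the eGFR drops below 60 or if the serum creatinine rises by ≥3.0 mg/dl the dapagliflozin will be stopped", with discontinuation from the study.

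Item 6 repeats a monitoring provision for each of Studies 1, 2 and 3: "Basic metabolic panel will be performed during the study to monitor renal function".

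**The concern.** An exclusion threshold has to sort every candidate in or out. This one carries a tolerance that is not defined anywhere, and it sits beside a stopping rule on the same measurement that has none. Two coordinators applying Item 7 in good faith could reach opposite decisions on the same candidate. One permitted reading admits people who already meet the value at which the protocol would stop the drug.

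A coordinator screening from Item 5, where the template asks for the exclusion criteria, would not see the eGFR bar at all.

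What is at stake is consistent eligibility decisions, and the safety purpose that Item 7 itself gives for the exclusion: symptomatic hypotension in people with impaired renal function.

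**Working it through.** The plan states no derived figure to reproduce. The check sets the rules side by side and does interval arithmetic on the thresholds.

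**Inputs**
- Entry rule (Item 7, Hypotension): excluded if eGFR is below 60 ±5.
- Stopping rule (Item 7, Renal Function): stop if eGFR falls below 60, with no tolerance.
- Item 5: creatinine and urine albumin limits only.

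**Step 1: possible entry cut-offs.** Lower: 60 − 5 = 55. Nominal: 60. Upper: 60 + 5 = 65. Below 55 a candidate is barred on every reading, and at 65 or above is not barred on any. Between them lies a band 65 − 55 = 10 units wide in which the decision depends on the reading.

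**Step 2: entry cut-off minus stopping value.**

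| Reading of entry cut-off | Minus stopping value | Consequence |
|---|---|---|
| 55 | 55 − 60 = −5 | Subjects from 55 to just under 60 enter already below the stopping value |
| 60 | 60 − 60 = 0 | No conflict, but no room for a fall |
| 65 | 65 − 60 = +5 | No conflict; 5 units of room |

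**Step 3: two example candidates.**

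| eGFR at screening | Cut-off 55 | Cut-off 60 | Cut-off 65 |
|---|---|---|---|
| 57 | eligible | barred | barred |
| 62 | eligible | eligible | barred |

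The candidate at 57 who enters on the 55 reading also exposes a gap in the stopping rule. That rule describes a fall to below 60, and this subject starts there. Either the subject is discontinued at the first metabolic panel, or the rule never operates for that subject. The text does not say which.

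**Step 4: does another section settle it?** No. The same wording stands in all three procedure rows, and the sentence describing the at-risk group uses the same 60 ±5. Item 5 gives no eGFR number, and the general-health criterion sets none.

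**Step 5: the expected fall.** Item 7 expects a small initial decrease in eGFR on the drug but gives no size. With entry at exactly 60, a subject entering just above that value could meet the stopping rule through the expected change alone. How often cannot be computed from the documents.

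**The case against.** The strongest reply is that little is at risk. The rules are cumulative, so the Item 7 bar binds even though Item 5 omits it, and no rule is absent from the protocol. Each subject takes at most three single 10 mg doses on separate days within 1-2 weeks. Ten of the 30 subjects receive placebo, and renal function is checked in each study. All of this stands and limits the weight of the point.

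It can also be said that the clash with the stopping rule is conditional, and that a stopping value of 60 in the very next paragraph makes 55 the least natural reading. That is fair: on 60 or 65 nothing contradicts. The ±5 might also be meant as measurement tolerance or room for investigator judgement. No section says so, and the stopping rule carries no matching allowance. A binding rule without a value still cannot be applied uniformly.

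A reader might infer something stronger: that the Item 5 creatinine limits let in a substantial group with clearly reduced eGFR. The documents do not support that. They name no eGFR equation, print no creatinine unit in Item 5 and give no creatinine distribution. As illustration only, assume mg/dl and take five variants of common creatinine-based equations (CKD-EPI 2009 and MDRD, each with and without the race term, and CKD-EPI 2021). A 50-year-old woman at 1.4 would then have eGFR of about 40 to 51, and a 50-year-old man at 1.5 about 49.5 to 62.0. The male range straddles 60, so the comparison depends on an equation that the protocol does not specify. Item 7 bars such people in any case. The point does not rest on these figures.

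Nor do the documents support reading this as a threat to the EGP comparison; no such effect is shown.

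**Conclusion.** The point holds as a minor matter of safety and conduct. A stated safety threshold for entry has no single value: the decision is undetermined for eGFR from 55 to just under 65. On one of the three readings, the 55 reading, subjects from 55 to just under 60 may be dosed while already below the protocol's own stopping value. Separately, the eGFR bar is missing from the list where eligibility is set out.

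This rests only on the wording of Items 5 and 7 and needs no eGFR equation. How many of the 30 planned subjects would fall in the band is unknown.

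**What to change.** 1. Delete ±5 from the eGFR text in all three Item 7 rows, both in the entry rule and in the description of the at-risk group.
2. State one exact eGFR entry cut-off, no lower than the stopping value of 60.
3. List that cut-off among the Item 5 exclusions as well as in Item 7. Name the eGFR equation and print the creatinine unit.
4. Have the investigators decide, and record, whether entry should be somewhat above 60, so that subjects are not discontinued merely for the small initial fall that Item 7 expects. The documents give no size for that fall, so the margin is a clinical judgement.

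The cost is a wording amendment and possibly a few more screen failures, more if a margin above 60 is chosen. Blood chemistries are already drawn at screening.
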